We recently performed a pilot study to evaluate the effects of alternate day fasting (ADF) and exercise, alone or combined, on various hepatic parameters in obese adults. ADF consists of a "fast day", in which 25% of energy needs (~500 kcal) are consumed, alternated with a "feed day", in which food is consumed ad libitum. Results from our pilot study show that the combination of ADF plus exercise produced greater reductions (-21 ± 9%) in alanine aminotransferase (ALT; an indirect marker of hepatic steatosis), compared to ADF alone (-13 ± 4%), or exercise alone (-16 ± 7%) after 12 weeks. Greater decreases in insulin resistance, HbA1c, LDL cholesterol, and more pronounced increases in HDL cholesterol, were observed in the combination group versus individual interventions. Data from our pilot trial also suggest that these decreases in insulin resistance by ADF plus exercise may be mediated in part by changes in hepatocyte-derived hormones (fetuin-A and FGF-21) that occur with liver fat reduction. Although these pilot findings are very promising, these data still require confirmation by a larger-scale (n = 360), longer-term (24 week) clinical trial. Accordingly, the specific aims of this study are:

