## 3.0 Objective/Aims

**Specific aim 1:** To compare the effects of a combination intervention (ADF and aerobic exercise) versus ADF or exercise alone on hepatic steatosis over 24-weeks in prediabetic obese NAFLD subjects.

**Hypothesis 1:** The combination group will experience greater reductions in hepatic steatosis (measured by MRS) when compared to the ADF group and the aerobic exercise group.

**Specific aim 2:** To compare the effects of a combination intervention (ADF and aerobic exercise) versus ADF alone or aerobic exercise alone on hepatokine profile over 24-weeks in prediabetic obese NAFLD subjects.

**Hypothesis 2:** The combination group will experience greater decreases in hepatokines with negative metabolic actions (fetuin-A, fetuin B, FGF-21, RBP4, selenoprotein P) and greater increases in hepatokines with positive metabolic actions (SHBG, adiponectin) when compared to the ADF group and the exercise group.

**Specific aim 3:** To compare the effects of a combination intervention (ADF and aerobic exercise) versus ADF alone or aerobic exercise alone on hepatic insulin sensitivity, insulin resistance, HbA1c, and other metabolic disease risk variables over 24-weeks in prediabetic-obese NAFLD subjects.

**Hypothesis 3:** The combination group will experience greater improvements in hepatic insulin sensitivity, insulin resistance and HbA1c and other metabolic disease variables (fasting glucose, insulin, plasma lipids, blood pressure, TNF- $\alpha$ , IL-6) when compared to the ADF group and the exercise group.

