Subjects who meet all the inclusion/exclusion criteria will be invited to participate in the study. Eligible subjects will be randomized by way of a stratified random sample. The sample frame will be divided into strata based on BMI, sex, and age. Subjects from each stratum will then be randomized to 1 of 4 groups: 1) ADF, 2) aerobic exercise, 3) combination (ADF plus aerobic exercise), or 4) control. **A total of n = 360 subjects (n = 90 per intervention group) will be recruited.** All the subjects will have the right to withdraw from the study at any time.

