## 6.0 Study design and procedures

A 24-week randomized, controlled, parallel-arm feeding trial will be implemented to test the effects of ADF and exercise, alone and in combination, on hepatic steatosis/fibrosis, hepatokines, hepatic insulin sensitivity, and other metabolic disease variables. Obese individuals with NAFLD (n = 360) will be randomized to 1 of 4 groups: (1) ADF (fast day: 25% energy intake, feed day: ad libitum fed, no exercise), (2) exercise (ad libitum fed, training 5 days/week), (3) combination (ADF plus exercise), and (4) control (ad libitum fed, no exercise). Changes in hepatic steatosis will be measured by MRS, and hepatic insulin sensitivity will be assessed by OGTT testing and the Matsuda Index. All study activities will be carried out at the Human Nutrition Research Unit (HNRU) located in the Applied Health Sciences Building ([name]).

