### Diet and exercise interventions

Group	Diet protocol	Exercise protocol
Combination (n = 45)	Fast day: 25% energy intake Feed day: Ad libitum fed	5 days/week, supervised 60 minutes, Intensity: 85% HRmax
ADF (n = 45)	Fast day: 25% energy intake Feed day: Ad libitum fed	No exercise
Exercise (n = 45)	Every day: Ad libitum fed	5 days/week, supervised 60 minutes, Intensity: 85% HRmax
Control (n = 45)	Every day: Ad libitum fed	No exercise

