## 12.0 Statistical considerations

All continuous variables will be examined for distributions and the presence of outliers. Variables that are not normally distributed will be transformed and if normality cannot be achieved, will be analyzed using non-parametric tests. Standardized descriptive statistics including measures of means, median, standard deviations, ranges, and standard errors for continuous variables within each group will be calculated to describe the groups at fixed time points. Differences between groups at baseline will be assessed by a one-way ANOVA. A repeated measures ANOVA will be used to evaluate the effects of diet, exercise, and their interaction (diet x exercise) on dependent variables; a significant interaction will be interpreted with a Bonferroni correction for multiple comparisons. A multivariate analysis that adjusts for the effects of confounding variables (age, sex, race, and baseline hepatic steatosis, hepatic insulin sensitivity, hepatokine profile, body weight, and body composition) will also be performed. Relations between continuous variables will be assessed by Pearson's or Spearman's correlation coefficients as appropriate. Data will be analyzed using SPSS software (SPSS, Chicago, IL).

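### Hypotheses 1 to 3 claim that the combination beats ADF alone and exercise alone, but Section 12.0 names no test of either contrast, and its main effects estimate something else

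*Combined protocol and SAP*

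**What the plan says.** Section 3.0 states Hypothesis 1 as "The combination group will experience greater reductions in hepatic steatosis (measured by MRS) when compared to the ADF group and the aerobic exercise group". Hypotheses 2 and 3 make the same two comparisons for hepatokines and for insulin sensitivity and metabolic variables, and Section 1.0 repeats all three. Section 6.0 gives a more general purpose, "to test the effects of ADF and exercise, alone and in combination".

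The only analysis text is Section 12.0. It plans a repeated measures ANOVA covering "the effects of diet, exercise, and their interaction (diet x exercise) on dependent variables; a significant interaction will be interpreted with a Bonferroni correction". Bonferroni-corrected multiple comparisons are mentioned once, as the way to interpret a significant interaction, and the comparisons are not listed. There is no rule for a non-significant interaction. The adjusted analysis and the non-parametric fallback name no contrast either. No alpha, effect size, SD or power is stated.

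**The concern.** The trial's central claim is that the combination beats each single treatment. A 2x2 analysis of main effects and interaction answers a related but different question, because half of each main effect is a single treatment compared with control, which no hypothesis mentions.

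Two problems follow. Read loosely, the plan lets two significant main effects with a non-significant interaction be reported as support for the hypothesis, even when the combination is no better than the better single treatment. Read strictly, the arm comparisons open only after a significant interaction. Yet the combination can beat both single treatments with no interaction at all.

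**Working it through.** **1. What the main effects estimate.** Let K, A, E and C be mean changes from baseline for combination, ADF, exercise and control. This change-score reading is the one most favourable to the plan. Let I = K - A - E + C.

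- Diet main effect = [(K - E) + (A - C)]/2 = (K - E) - I/2.
- Exercise main effect = [(K - A) + (E - C)]/2 = (K - A) - I/2.

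These identities do not depend on SD or correlation. A main effect equals its hypothesised contrast only if I = 0. Sub-additive effects make it overstate the contrast; super-additive effects make it understate the contrast.

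**2. The plan's pilot figures.** Section 2.0 reports that the combination "produced greater reductions (-21 ± 9%) in alanine aminotransferase" "compared to ADF alone (-13 ± 4%), or exercise alone (-16 ± 7%) after 12 weeks". The control change, c, is not given. Then I = -21 + 13 + 16 + c = 8 + c, where a positive value is sub-additive because reductions are negative.

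| Assumed c | I | Diet main effect (contrast K - E = -5) | Exercise main effect (contrast K - A = -8) |
|---|---|---|---|
| -8 | 0 | -5 | -8 |
| -4 | 4 | -7 | -10 |
| 0 | 8 | -9 | -12 |
| +4 | 12 | -11 | -14 |

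The point estimates are additive only if control ALT fell by 8 points. On a ratio scale with a flat control, 0.87 x 0.84 = 0.731 would be expected against 0.79 observed; the control ratio would have to be 0.731/0.79 = 0.925, a 7.5% fall.

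**3. False support (illustrative).** Assumptions: two-sided 5%; one change score with SD 1; pooled variance on 4(n - 1) df; 400,000 replicates; main effects and contrasts counted only in the favourable direction. Section 5.0 says "A total of n = 360 subjects (n = 90 per intervention group) will be recruited", but the Section 6.0 intervention table shows 45 per arm, so both are used. Standard errors in SD units are sqrt(2/n) for a contrast, sqrt(1/n) for a main effect and sqrt(4/n) for the interaction. Here 'support' means both main effects significant and the interaction not significant.

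| True effects against control (SD) | 90/arm | 45/arm |
|---|---|---|
| All three active arms 0.3 | 6% | 2% |
| All three 0.5 | 15% | 9% |
| All three 0.8 | 3% | 14% |
| Combination and better arm 0.5, other 0.3 | 19% | 9% |
| Combination and better arm 0.8, other 0.4 | 25% | 19% |
| Combination and better arm 0.8, other 0.5 | 22% | 22% |

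Requiring both direct contrasts gives about 0.5% in the first three rows and 1.4% to 2.5% in the last three.

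The ceilings follow by algebra. When all active arms are equal, each main effect and the interaction have the same power p, so the rate is about p²(1 - p), with maximum 4/27 = 15%. When the combination equals the better arm and the other arm's effect is e, the smaller main effect is e/2 and the interaction has size e with twice the standard error. Both again have power p, and once the larger main effect is almost always significant the rate is about p(1 - p), with maximum 25%.

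**4. The strict reading.** With exactly additive effects of 0.5 SD and 90 per arm, both direct contrasts are significant in 86% of simulated trials, but in only 2.9% if the interaction must be significant too.

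**The case against.** A 2x2 ANOVA is standard for this layout and suits the general purpose in Section 6.0. The Bonferroni clause most naturally means comparing arms, which would include both contrasts, and Section 12.0 does not forbid other comparisons. That stands: the contrasts are unspecified, not excluded. The follow-up also helps when sub-additivity is large: with all active arms at 0.8 SD and 90 per arm the interaction is significant in about 97% of trials, which is why false support falls to 3%. It helps little at intermediate effects, and it fails when effects are additive.

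The rule behind the false-support figures is not in the plan. That also stands: they show what the gap permits and are not the plan's error rate.

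The pilot evidence is weak. It is 12-week ALT rather than MRS liver fat, and the ± is undefined. If it is a standard error, the interaction's standard error is at least sqrt(81 + 16 + 49) = 12 points before control variance is added, so the pilot neither shows nor rules out additivity. The argument does not need the pilot; the identity in step 1 is enough.

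**Conclusion.** The concern holds. The plan states two contrasts per hypothesis and specifies a test of neither. That mismatch, and the half-interaction difference, are exact and rest on no assumption. The size of the distortion is conditional: 4 ALT points on each main effect if the pilot control was flat, and 0 to 6 points for control changes from -8 to +4. The 2% to 25% false-support range depends on the assumed decision rule, alpha and effect sizes, and on a single change score rather than the full repeated measures model. The point should be fixed before analysis because it leaves the trial's main claim to the analyst's choice of test.

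**What to change.** In Section 12.0, name combination minus ADF and combination minus exercise, in week-24 change in hepatic steatosis, as the primary contrasts. Estimate them from the planned four-arm model and test them whatever the interaction result. If the claim is that the combination beats both, test each at two-sided 0.05 and require both; use 0.025 each only if a win on either alone would be claimed. Report the interaction and main effects as secondary, with confidence intervals. Use the same contrasts for Hypotheses 2 and 3; multiplicity across their many outcomes is a separate matter.

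This is one or two sentences, with no new data or patients. The cost is power relative to main-effect rules (same simulation assumptions):

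| True effects | n/arm | Both contrasts | Both main effects | Both main effects, interaction not significant |
|---|---|---|---|---|
| Additive, 0.5 SD | 90 | 86% | 99% | 95% |
| Additive, 0.5 SD | 45 | 50% | 84% | 80% |
| Additive, 0.3 SD | 90 | 35% | 66% | 62% |
| Additive, 0.3 SD | 45 | 15% | 27% | 26% |
| Single arms 0.5 SD, interaction -0.2, true contrast 0.3 | 90 | 35% | 93% | 79% |
| Single arms 0.5 SD, interaction -0.2, true contrast 0.3 | 45 | 15% | 58% | 52% |

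In the last two rows the main-effect columns are power for an effect of 0.4 SD, not for the hypothesised 0.3. The 90 and 45 per arm figures must be reconciled separately, since they determine which rows apply.

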## Summary of intervention groups and key outcome measures

## Study activities

Study activities	Study visits (week of study)																								
	Screen	1	2	3	4	5	6	7	8	9	10	11	12	13	14	15	16	17	18	19	20	21	22	23	24
Informed consent	•																								
Screening questionnaire	•																								
Michigan Alcohol Screening test	•																								
Pregnancy test	•	•																							•
Body weight (at home)	•	•	•	•	•	•	•	•	•	•	•	•	•	•	•	•	•	•	•	•	•	•	•	•	•
Blood draw	•	•																•							•
Blood pressure/heart rate		•																•							•
Body composition (BIA)		•																•							•
Waist circumference		•																•							•
Body composition (DXA)		•																•							•
Activity monitor		•																•							•
Hepatic insulin sensitivity (OGTT)		•																•							•
Hepatic steatosis (MRS)		•																•							•
Food record	•	•																•							•
Sleep questionnaires		•																•							•
Time per visit:	1	4	0	0	0	0	0	0	0	0	0	0	0	0	0	0	0	0	0	0	0	0	0	0	4

**Body weight, blood pressure, heart rate:** Body weight measurements will be taken weekly with subjects wearing light clothing and without shoes using a balance beam scale at home. Digital scales will be provided to each subject. Height will be assessed using a wall-mounted stadiometer at week 1. BMI will be assessed as kg/m^2. Blood pressure and heart rate will be assessed at week 1, 13, 24.

**Body composition:** Dual energy X-ray absorptiometry (DXA) will be performed on all subjects at week 1, 13, and 24 (iDXA, GE Inc) to assess fat mass, fat free mass, and visceral fat mass. Percentage body fat will be assessed in triplicate using a tetra-polar bioelectrical impedance analyzer each week (Omron HBF-500; Omron Health Care, Bannockburn, IL). Waist circumference will be measured weekly.

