**Metabolic disease risk factors:** Plasma metabolic disease risk factors will be assessed at baseline week 1, 13, and 24. Plasma total cholesterol, LDL cholesterol, HDL cholesterol, and triglyceride concentrations will be measured in duplicate using enzymatic kits, standardized reagents, and standards (Biovision Inc, Mountainview, CA) and analyzed using a microplate reader (iMark Microplate Reader; Bio-Rad Laboratories Inc, Richmond, CA). HbA1c will be assessed by ELISA (Mybiosource, San Diego, CA). Fasting plasma glucose concentrations will be measured with a hexokinase reagent kit in duplicate (A-agent glucose test, Abbott, South Pasadena, CA). Fasting insulin will be measured as total immunoreactive insulin (Coat-A-Count Insulin, Los Angeles, CA). Insulin resistance (IR) will be calculated by the HOMA (Homeostasis Model Assessment) method:  $[HOMA-IR = \text{Fasting insulin } (\mu\text{U/ml}) \times \text{Fasting glucose } (\text{mg/dL}) / 405]$ .

**Proteomics and metabolomics:** Plasma-derived proteomic and metabolomic outcomes will be measured using immunoassay and mass spectrometry, as described previously.

**Hepatokine plasma levels:** Plasma hepatokines will be measured at week 1, 13, and 24. Commercially available ELISA kits will be used to measure concentrations of Fetuin-A, fetuin-B, FGF-21, SHBG, and RBP4, (R&D Systems, Minneapolis), and adiponectin and selenoprotein P (Mybiosource, San Diego, CA). All samples will be assessed in duplicate.

**Inflammation:** Inflammatory markers will be measured at week 1, 13, and 24. C-reactive protein (CRP) will be measured in duplicate using Immulite 1000 High Sensitivity CRP kits (Diagnostic Products Corporation, Los Angeles, CA). Adiponectin, leptin, TNF- $\alpha$ , and IL-6 will be measured using ELISA (R&D Systems, Minneapolis, MN).

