## 9.0 Data analysis

Data will be analyzed by [name] PhD (Biostatistician) and [name] by SPSS software (SPSS v24).

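### The additional adjusted analysis uses about 13 measured baseline values with no rule for a missing one, so a complete-case fit would drop participants who have outcome data

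*Combined protocol and SAP*

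**What the plan says.** Section 12.0 names a repeated measures ANOVA for diet, exercise and their interaction. It then adds a second analysis: "A multivariate analysis that adjusts for the effects of confounding variables", with the covariates given as "age, sex, race, and baseline hepatic steatosis, hepatic insulin sensitivity, hepatokine profile, body weight, and body composition". It does not name the model, the outcomes covered or the variables that stand for each domain.

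Other sections show what the domains contain:
- **Hepatokines:** Hypothesis 2 in Section 3.0 lists five with negative metabolic actions ("fetuin-A, fetuin B, FGF-21, RBP4, selenoprotein P") and two with positive actions ("SHBG, adiponectin"). Section 6.0 gives their timing: "Plasma hepatokines will be measured at week 1, 13, and 24".
- **Body composition:** Section 6.0 uses DXA "to assess fat mass, fat free mass, and visceral fat mass".
- **Steatosis and insulin sensitivity:** Section 6.0 takes one value from MRS and one from the Matsuda index.

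Sections 9.0 and 12.0 name SPSS as the software. The documents contain no rule for missing covariates, no imputation method, no analysis population, and no expected rate of dropout or missing baseline data.

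**The concern.** A regression with many covariates, fitted to complete cases, needs every covariate to be present. A participant with good MRS scans at all visits but no baseline value for one hepatokine would be left out of the adjusted steatosis comparison, although that hepatokine matters little to it.

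Two things are at stake. The first is precision, in an analysis usually done to gain it. The second is interpretation: if adjusted and unadjusted results differ, a reader cannot tell whether the adjustment or the change of sample is responsible.

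The list also has a gap. It contains the baselines of steatosis, hepatic insulin sensitivity and the hepatokines, but not those of several Aim 3 outcomes: HbA1c, HOMA-IR, fasting glucose and insulin, lipids, blood pressure, TNF-α and IL-6. For these, the list names other outcomes' baselines and not the outcome's own, which is usually the most useful covariate.

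**Working it through.** **The plan's own figure.** Section 5.0 gives 4 × 90 = 360, which is consistent. It cannot be derived further, because no alpha, power, effect size, SD or dropout rate is stated. There is no missing-data figure to reproduce.

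**Number of measured baseline values.** MRS 1 + Matsuda 1 + hepatokines 7 + body weight 1 + DXA 3 = 13. Adding impedance percent fat makes 14, and waist 15. Age, sex and race are taken as always known.

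**Assumptions, none of them in the documents.** The fit is complete-case. A share m of participants lacks each value (or each domain), with m = 1%, 2% or 3%. Comparison power with nobody lost is 90% at two-sided 5%.

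**Formulas.** With k units missing independently, the share kept is (1 − m)^k. The standard error rises by 1/√kept. Power = Φ(3.2415 × √kept − 1.96), where 3.2415 = 1.2816 + 1.9600.

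Three patterns of missingness:
- k = 13: every value goes missing independently.
- k = 5: each of the five domains goes missing as a block.
- k = 1: all gaps fall in the same people.

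| m | k | Lost | Kept of 360 | SE factor | Power |
|---|---|---|---|---|---|
| 1% | 13 | 12.2% | 316 | 1.07 | 85.9% |
| 1% | 5 | 4.9% | 342 | 1.03 | 88.5% |
| 1% | 1 | 1.0% | 356 | 1.01 | 89.7% |
| 2% | 13 | 23.1% | 277 | 1.14 | 81.1% |
| 2% | 5 | 9.6% | 325 | 1.05 | 86.9% |
| 2% | 1 | 2.0% | 353 | 1.01 | 89.4% |
| 3% | 13 | 32.7% | 242 | 1.22 | 75.8% |
| 3% | 5 | 14.1% | 309 | 1.08 | 85.2% |
| 3% | 1 | 3.0% | 349 | 1.02 | 89.1% |

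Example: 1 − 0.97^13 = 0.327, and Φ(3.2415 × √0.673 − 1.96) = Φ(0.70) = 0.758.

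**Partial clustering.** When the 13 indicators of missingness share a latent normal factor, simulated loss at m = 3% is 24.6%, 19.1% and 11.0% for latent correlations of 0.3, 0.5 and 0.8.

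**Sample size conflict.** The intervention table in Section 6.0 shows 45 per group (180 in total), against 90 per group in Section 5.0. The percentages do not depend on this, but the counts do: at 32.7% loss, 180 becomes about 121.

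**The case against.** **The loss may be small.** The seven hepatokines come from plasma taken at the same visits, the three DXA values from one scan, and weight is also recorded at screening and weekly. Assays are run in duplicate and plasma is stored frozen, so a failed assay might be repeated. People with claustrophobia or implanted devices, a plausible cause of failed scans, are excluded at entry. This stands, and it makes full independence across 13 values unlikely. It does not remove the problem: the hepatokine kits are separate and come from two suppliers, so some failures can be isolated, and the block calculation still loses 4.9% to 14.1%.

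**A reader might infer that a third of participants will be lost.** The documents do not support that. It needs an assumed 3% missing per value together with independence. It is not a ceiling either, since 5% would give 48.7%.

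**A reader might infer that the adjusted comparison is biased.** That is too strong. A covariate measured before treatment is missing independently of arm, so complete cases still form a randomised comparison, only in fewer and somewhat different people.

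**The model is inferred.** Section 12.0 does not say that all covariates enter together, that the same set serves every outcome, or that missing cases are deleted. That is fair. Thirteen is a reading of the list, and deletion is an assumption about the software default. If the adjusted model kept baseline among its repeated measurements, the outcome's own baseline would already be used. The text leaves all of this open, which is the point.

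**The analysis is additional.** True. The repeated measures ANOVA stands whatever happens to the covariates.

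**Conclusion.** The point holds as a gap in specification. Section 12.0 commits to an adjusted analysis on about 13 measured baseline values and gives no rule for a missing one. Under complete-case fitting, the loss is about 5% to 12% at an assumed 1% missing and 14% to 33% at 3%, with the lower ends for domain blocks and the upper ends for full independence. An assumed 90% power falls to about 86% to 88.5% and 76% to 85% respectively. If all gaps fall in the same people, the loss is 1% to 3% and hardly matters.

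The consequence is limited to precision and to comparability with the unadjusted result. Overlap among the covariates, such as weight with fat and fat-free mass, does not bias the arm contrast, so it is no reason to require a shorter list.

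**What to change.** Add two statements to Section 12.0:

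1. In every adjusted model, a missing pre-treatment baseline covariate is replaced by the mean of that covariate over all arms, so no participant with outcome data is excluded for a missing covariate. The rule applies only to values taken before the assigned intervention starts.
2. Each outcome's adjusted model includes that outcome's own baseline value, including the Aim 3 outcomes whose baselines are not on the list. The response should then be the follow-up value, so that a participant without a baseline still has a response.

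The timing condition in (1) needs confirming. Baseline measures are scheduled at week 1, when fasting and training also begin (Section 6.0), and the blood sampling paragraph refers to feed and fast days. The documents should state whether week 1 measurements precede the first day of intervention. If some do not, mean replacement should not be used for them on this argument.

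The cost is a few sentences and no change to trial conduct. Removing other listed covariates is optional: it simplifies the model but gives up whatever precision they add, and it is not part of this change.

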## 1.0 Project Summary/Abstract

**Background:** Approximately 65% of obese individuals have non-alcoholic fatty liver disease (NAFLD), and this condition is strongly related to the development of insulin resistance and diabetes. Innovative lifestyle strategies to treat NAFLD are critically needed. Alternate day fasting (ADF) has been shown in animals to reduce hepatic steatosis and improve hepatic insulin sensitivity, but these findings have yet to be confirmed in human subjects. ADF consists of a “feast day” where individuals are permitted to consume food *ad libitum*, alternated with a “fast day” where individuals consume 25% of their usual intake (~500 kcal). We performed a pilot study to evaluate the effects of ADF combined with exercise, versus ADF or exercise alone, on hepatic parameters in obese patients. Our results show that the combination of ADF plus exercise produced greater reductions in alanine aminotransferase (ALT; an indirect marker of hepatic steatosis), compared to ADF alone, or exercise alone, after 12 weeks. Greater decreases in insulin resistance, HbA1c, LDL cholesterol, and more pronounced increases in HDL cholesterol, were observed in the combination group versus individual interventions. Data from our pilot trial also suggest that these decreases in insulin resistance may be mediated in part by changes in hepatocyte-derived hormones (hepatokines) that occur with liver fat reduction. Although these pilot findings are very promising, these data still require confirmation by a well powered longer-term (24 week) clinical trial.

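### Correlations between outcomes are planned without regard to randomised arm, so changes pooled over four arms can correlate even when unrelated within arms

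*Combined protocol and SAP*

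**What the plan says.** Section 12.0 gives relations between outcomes one sentence: "Relations between continuous variables will be assessed by Pearson's or Spearman's correlation coefficients as appropriate". It names no variable pairs and no time point. It does not choose between levels and changes, and it does not say whether arms are pooled.

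Two neighbouring sentences might seem to fill the gap, but neither does:

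- Group is mentioned for the descriptive statistics, which "for continuous variables within each group will be calculated to describe the groups at fixed time points". That does not extend to the correlations.
- A separate multivariate analysis "adjusts for the effects of confounding variables (age, sex, race, and baseline hepatic steatosis, hepatic insulin sensitivity, hepatokine profile, body weight, and body composition". Arm is not in that list, and the list is not tied to the correlations.

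Section 9.0 adds only the analysts and the software. On design, Section 5.0 states "Subjects from each stratum will then be randomized to 1 of 4 groups". Hypotheses 1-3 in Section 3.0 predict larger changes with the combination than with either single intervention in steatosis, hepatokines and insulin resistance.

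The background carries a mechanistic idea from the pilot: "these decreases in insulin resistance may be mediated in part by changes in hepatocyte-derived hormones (hepatokines) that occur with liver fat reduction" (Section 1.0, repeated in similar words in Section 2.0). No aim or hypothesis takes it up, and no mediation analysis is planned.

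**The concern.** A correlation computed over all participants mixes two things. One is the relation within arms: whether people whose hepatokines changed more than others in their arm also had a larger change in insulin resistance. The other is the relation between arm means, which is non-zero whenever treatment moves both markers. Only the first says anything about how the markers are linked beyond their shared response to treatment.

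The trial is designed in the hope that several outcomes will differ by arm, so the condition for the artefact is one the hypotheses themselves predict. Apart from adjustment for baseline values, this sentence is the only stated method relating one outcome to another. A reader of the results could take a significant pooled coefficient as bearing on the pilot's mechanism when it only restates that the interventions moved both variables.

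**Working it through.** **Inputs from the documents.** There are four arms (Section 5.0). Section 5.0 also states "A total of n = 360 subjects (n = 90 per intervention group) will be recruited", while the intervention table in Section 6.0 lists "Combination (n = 45" and 45 for each other arm. No effect size, SD or significance level is given for these analyses, so there is no figure in the plan to reproduce.

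**Assumptions.** Equal arm sizes, within-arm SD of 1 for each marker, true within-arm correlation of 0, identical arm shifts on both markers, two-sided 0.05.

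**Formula.** Let B be the variance of the four arm means in within-arm SD units. The pooled covariance is B and each pooled variance is 1 + B, so r = B/(1 + B). In general, r = C/√[(1 + Vx)(1 + Vy)], with C the between-arm covariance and V the between-arm variances.

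**Main case.** Shifts of 0, 0.4, 0.6 and 1.0 SD have mean 0.5. B = (0.25 + 0.01 + 0.01 + 0.25)/4 = 0.13, and r = 0.13/1.13 = 0.115.

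**Check by Fisher's z.** With n = 360, √(360 − 3) = 18.89 and atanh(0.115) = 0.1155. The product is 2.18, and the chance of exceeding 1.96 is Φ(2.18 − 1.96) = 0.59. With n = 180, √177 = 13.30 and the product is 1.54, so the chance is Φ(1.54 − 1.96) = 0.34. The expected r is the same at both sizes; only the chance of significance falls.

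**Simulation, 90 per arm, 4,000 trials per row:**

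| Arm shifts (SD) | B | Pooled r | Pooled Pearson, p < 0.05 | Adjusted for arm, p < 0.05 |
|---|---|---|---|---|
| 0, 0.2, 0.3, 0.5 | 0.0325 | 0.031 | 8.5% | 4.7% |
| 0, 0.4, 0.6, 1.0 | 0.13 | 0.115 | 59.5% | 5.6% |
| 0, 0.6, 0.9, 1.5 | 0.2925 | 0.226 | 99.5% | 5.0% |

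**Other patterns, 1,500 trials each, pooled Pearson significant at 90 / 45 per arm:**

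| Combination effect | Single arms at half the combination effect | All active arms equal |
|---|---|---|
| 0.3 SD | 5% / 5% | 7% / 4% |
| 0.5 SD | 8% / 8% | 14% / 10% |
| 0.8 SD | 32% / 16% | not run |
| 1.0 SD | 55% / 33% | 85% / 58% |

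Spearman behaves much like Pearson (53% against 55% at 90 per arm with a 1.0 SD combination effect and single arms at half). If only one marker responds, C = 0, so r = 0, and 4-5% of trials are significant. The arm-adjusted coefficient was significant in about 3-6% of trials in every scenario, which is 5% up to simulation error.

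**The documents' only change figures.** Section 2.0 gives pilot ALT changes of −21 ± 9%, −13 ± 4% and −16 ± 7% for combination, ADF and exercise, without saying whether ± is SD or SEM. For illustration, apply this pattern to both markers with no change in controls. The arm means 0, 13, 16 and 21 have variance 60.25, and the mean squared ± value is (81 + 16 + 49)/3 = 48.67.

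- Read as SD: B = 60.25/48.67 = 1.24, r = 0.55, and every simulated trial (500 run) was significant.
- Read as SEM with an assumed 16 to 25 per pilot arm: r = 0.07 to 0.05, with 28% to 13% significant.

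The documents therefore do not settle the size.

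**The case against.** A reader might infer that the plan will pool all participants, that the markers will then correlate whatever the truth, and that the trial will declare the hepatokine mechanism confirmed. The documents support none of these steps.

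- **Pooling is inferred from silence.** The sentence equally allows within-arm or baseline correlations, and baseline values carry no treatment effect.
- **The artefact is conditional.** Both markers must differ between arms by a sizeable amount. At about 0.3 SD it is negligible.
- **Mechanism is not a planned conclusion.** It is a hedged background remark: "these decreases in insulin resistance by ADF plus exercise may be mediated in part by changes in hepatocyte-derived hormones". Aims 1-3 are all comparisons between arms.
- **The magnitudes are assumed.** Identical shifts on both markers align the arm patterns perfectly. Even then, r of 0.115 and 0.226 correspond to about 1% and 5% of shared variance (0.115² = 0.013; 0.226² = 0.051), which is thin evidence for any mechanism.
- **Arm adjustment does not establish mediation.** Shared drivers such as weight loss or adherence remain within arms.

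All of this stands, and it limits the point to a secondary analysis. It does not remove it. The wording permits a pooled analysis of changes, the choice could be made after results are seen, and switching to Spearman gives no protection. An arm-adjusted coefficient removes the between-arm component directly.

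**Conclusion.** The point holds in conditional form. The stated method takes no account of arm, and if changes are pooled it can report correlations that reflect only a shared response to treatment. The share of trials with a false-positive correlation runs from near 5% when effects are small to about 59% in the main 1.0 SD case. It is higher if all active arms respond equally or effects are larger. These rates rest on the assumed shifts, the 0.05 level, zero within-arm correlation and 90 per arm. At 45 per arm the large-effect rates are lower, but the conclusion does not change. False support for the hepatokine mechanism is a risk in interpretation. The repeated measures ANOVA and the tests of Hypotheses 1-3 are not affected.

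**What to change.** Replace the correlation sentence in Section 12.0 with text along these lines: *Correlations between outcomes will use changes from week 1 to week 24, for variable pairs named in advance. They will be estimated as partial correlations adjusted for randomised arm (rank-based for skewed variables), or within each arm and pooled by Fisher's z. These analyses are exploratory. Unadjusted correlations pooled across arms will not be used as evidence of mechanism.*

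Adjustment for the baseline values of both variables is optional; the calculations above tested adjustment for arm only. Separately, reconcile the arm sizes in Section 5.0 and the intervention table.

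The cost is a few lines of text. No new data, visits or participants are needed, and partial correlation is available in the software already named.
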